## 11.4. Vital Signs

The vital signs data, including orthostatic blood pressures and heart rate (calculated as standing value minus sitting value), will be summarized with descriptive statistics by treatment group and visit. Sitting blood pressure and heart rate measurements were collected in triplicate at each visit throughout the study and the average of the triplicate values will be used for the purpose of summarization. If a subject has multiple standing vital signs collected during the same visit, the last one collected will be used to calculate whether the subject met criteria for orthostatic hypotension (defined as a drop from sitting to standing values in systolic BP of >20 mmHg or a drop from sitting to standing in diastolic BP of >10 mmHg). Observed and change from baseline values for the vital signs data and the number and percentage of subjects meeting the criteria for orthostatic hypotension will be summarized at each visit for the DB and OL periods separately.

## 11.5. Electrocardiogram

Descriptive statistics for the observed values and changes from baseline will be presented for each of the ECG parameters (heart rate, PR interval, QRS duration, QT interval, QTcF) by visit and treatment group.

Frequency tables (number and percentage of subjects) will be presented for the investigator overall categorical assessment (ie, Normal, Abnormal not Clinically Significant, or Abnormal Clinically Significant) by visit and treatment group.

Two additional categorical summaries (frequency tables displaying number and percentage of subjects) will be presented for the QTcF interval by treatment group. For the first summary, the observed QTcF values at each visit will be classified as follows:

- Greater than 450 msec
- Greater than 480 msec
- Greater than 500 msec

For the second categorical summary, the changes from baseline to each subsequent visit will be classified as follows:

- Increase greater than 30 msec
- Increase greater than 60 msec

The same categorical summaries will be presented in frequency tables for values at any postbaseline visit (including unscheduled and early termination visits) meeting the aforementioned criteria.

The above ECG summaries will be produced for the DB period and the OL period separately.

## 11.6. Columbia-Suicide Severity Rating Scale

The C-SSRS data will be presented in the following summaries:

- Screening/lifetime assessment
- Screening/past 6 months (suicidal ideation items); past 1 year (suicidal behavior items) assessment
- Baseline (Day 1) assessment

- Postbaseline assessments

Each summary will display the number and percentage of subjects who report “Yes” to specific C-SSRS items or categories of items (a category is assigned a “Yes” value if a “Yes” is reported for any item in the category). These C-SSRS items and categories are as follows:

- Suicidal Ideation Items
  - (1) Wish to be dead
  - (2) Non-specific active suicidal thoughts
  - (3) Active suicidal ideation with any methods (not plan) without intent to act
  - (4) Active suicidal ideation with some intent to act, without specific plan
  - (5) Active suicidal ideation with specific plan and intent
- Suicidal Ideation Category: Any of items (1) through (5)
- Suicidal Behavior Items
  - (6) Preparatory acts or behavior
  - (7) Aborted attempt
  - (8) Interrupted attempt
  - (9) Non-fatal suicide attempt
  - (10) Completed suicide (“Since Last Visit” assessments only)
- Suicidal Behavior Category: Any of items (6) through (10)
- Suicidal Ideation or Behavior Category: Any of items (1) through (10)

For the “all postbaseline assessments” summary, each subject’s C-SSRS responses for all postbaseline assessments will be evaluated, and a “Yes” response for any assessment will be considered as a “Yes” for the subject.

In addition to the summaries described above, shift tables comparing postbaseline suicidal ideation scores to baseline scores will be presented. The shift table scores are defined as the following:

- 0 = No suicidal ideation
- 1 = Wish to be dead
- 2 = Non-specific active suicidal thoughts
- 3 = Active suicidal ideation with any methods (not plan) without intent to act
- 4 = Active suicidal ideation with some intent to act, without specific plan
- 5 = Active suicidal ideation with specific plan and intent

The shift tables will display the number and percentage of subjects within each cell of a 6 x 6 table for each treatment group, with the rows representing the baseline score and the columns representing the maximum score recorded across all postbaseline assessments (including both scheduled and unscheduled visits). Subjects missing either a baseline score or all postbaseline scores will not appear in the table.

The above C-SSRS summaries will be produced for the DB period and the OL period separately.

## **11.7. Brief Psychiatric Rating Scale (BPRS)**

The Brief Psychiatric Rating Scale (BPRS) is a clinician-rated tool designed to assess the severity of psychopathology in subjects with schizophrenia and other psychotic disorders. The BPRS includes 18 items that address somatic concern, anxiety, emotional withdrawal, conceptual disorganization, guilt feelings, tension, mannerisms and posturing, grandiosity, depressive mood, hostility, suspiciousness, hallucinatory behaviors, motor retardation, uncooperativeness, unusual thought content, blunted affect, excitement, and disorientation. The severity of each of the 18 items of the BPRS is rated on a scale of 1 (not present) to 7 (extremely severe) (total score range: 18 to 126). Higher scores represent greater symptom severity. Items that are not scored are left blank (i.e., not score as “0”). Rather than using the EDC total score value, the total score for BPRS will be re-calculated as the sum of the ratings for each of the 18 items. Missing items will be imputed based on the average score of the other items at that assessment; however, if >50% of the items are missing for that subject/visit, then the total score will be set to missing.

BPRS total score observed and change from baseline values will be summarized with descriptive statistics by visit and treatment group. This summary will be produced for the DB period and the OL period separately. The study baseline will be used for the DB period summaries while the OL baseline will be used for the OL period summaries.

## **11.8. Prior and Concomitant Medications**

Prior medications and concomitant medications, including glucocorticoids and mineralocorticoids, will be summarized by World Health Organization (WHO) Drug Anatomical Therapeutic Chemical Classification (ATC) Level 3 category (or Level 2 if there is not an applicable Level 3 category) and preferred name. Concomitant medications will be summarized separately for the DB and OL periods.

Medications will be assigned to study periods (prior, concomitant in the DB period, and/or concomitant in the OL period) based on the medication start and stop dates relative to study drug dosing in the DB and OL periods. Medications that were started and stopped prior to the date of the first dose of study drug in the DB period will be assigned as prior. Medications that had a stop date or were ongoing during the DB period will be assigned as concomitant in the DB period. Medications that had a stop date or were ongoing during the OL period will be assigned as concomitant in the OL period.

Within each summary, the number and percentage of subjects using medications in each WHO Drug ATC category (Level 3/preferred name) will be summarized by treatment group. A subject may take the same medication more than once or multiple medications for a subject may be classified under the same ATC level or preferred name. A subject is counted only once for each level of medication classification within a summary. The tables will be sorted alphabetically by ATC code and then by preferred name.

## **12. PATIENT-REPORTED OUTCOMES**

Patient-reported outcomes (PROs) capture the status of a subject's health condition and come directly from the subject, without interpretation of the subject's response by a clinician or anyone else. The following section describes the PROs that were administered to subjects throughout the study and the methods of scoring and summarizing these data. All outputs for the PRO summaries will be based on the Full Analysis Set. The analysis of the PRO data will be based on descriptive statistics and presented by treatment group according to the study visit unless otherwise noted. PRO data will not be imputed. No formal hypothesis-testing analysis of PRO data will be performed. Unless otherwise noted, the below summaries will be produced for both the DB period and the OL period separately and will follow the treatment-period specific treatment group and baseline definitions (as described in Section 6) where the study baseline will be used for the DB period summaries and the OL baseline will be used for the OL period summaries.

### **12.1. 36-Item Short Form Health Survey (SF-36) V2**

The SF-36 is a multipurpose, short form health survey with 36 questions that yields an 8-scale profile of functional health and wellbeing, as well as two psychometrically based physical and mental health summary measures. It consists of 8 health concepts: vitality, physical functioning, pain, general health perception, physical role limitations, emotional role functioning, social functioning, and mental health. The standard 4-week recall is used in this study. Each domain is scored based on a weighted sum of the questions in their section, on a 0-100 scale (each section is weighted equally). The lower the score the worse the disability. Calculation of SF-36 V2 score is via a licensed scoring software. Observed and change from baseline values will be summarized descriptively for the 8 health concepts and the 2 summary measures by treatment group for the DB period and the OL period. The study baseline will be used for the DB period summaries, and the OL baseline will be used for the OL period summaries.

### **12.2. EuroQoL 5 Dimensions 5 Levels (EQ-5D-5L) and Visual Analog Scale (EQ-VAS)**

The EuroQol 5 Dimensions 5 Levels (EQ-5D-5L) is a general, single index measure for describing and valuing health. It defines health in terms of 5 dimensions: Mobility, Self-Care, Usual Activities, Pain/Discomfort, and Anxiety/Depression. Each dimension has 5 levels: no problems, slight problems, moderate problems, severe problems, and extreme problems. The subject indicates his/her health state by checking the box next to the most appropriate statement. Number and percentage of subjects in each of the 5 levels for each dimension at baseline and each postbaseline visit will be summarized by treatment group.

Subjects also rate their overall health on a 0 to 100 hash-marked, vertical visual analogue scale (EQ-VAS). The endpoints are labeled 'The best health you can imagine' (100) and 'The worst health you can imagine' (0). The EQ-VAS score at each visit and change from baseline to each postbaseline visit will be summarized by treatment group.

The above summaries will be produced for the DB period and the OL period. The study baseline will be used for the DB period, and the OL baseline will be used for the OL period summaries.

### **12.3. Multidimensional Assessment of Fatigue (MAF)**

The Multidimensional Assessment of Fatigue (MAF) is a 16-item scale that measures fatigue according to 4 dimensions: 1-degree and severity, 2-distress that fatigue causes, 3-timing of fatigue (over the past week, when it occurred and any changes), and 4-impact of fatigue on various activities of daily living (household chores, cooking, bathing, dressing, working, socializing, sexual activity, leisure and recreation, shopping, walking, and exercising). Subjects rate each item 1 through 14 using a 10-point numeric rating scale, and items 15 and 16 using categorical responses for timing. The results from the MAF are reported as a single score in the form of a Global Fatigue Index (GFI). Scores range from 1-no fatigue to 50-severe fatigue.

MAF scoring is a sum of the responses to questions 1-15. Item 16 is not included in the GFI. If respondents select 1 to question 1 (To what degree do you experience fatigue = “1 – not at all”), then they are instructed to stop the questionnaire, assign a score of 0 to items 2-16 and their score would be “1-no fatigue”. If respondents select anything besides 1, they continue to questions 2-16. The GFI is calculated by converting item 15 to a 0-10 scale by multiplying each score by 2.5, summing items 1, 2, and 3; and averaging items 4-14 and the newly score item 15. A score will not be assigned to items 4-14 if the subject gave a response of “do not do any activity for reasons other than fatigue.”

The GFI observed, change from baseline, and percent change from baseline values will be summarized descriptively by treatment group for the DB period and the OL period. The study baseline will be used for the DB period, and the OL baseline will be used for the OL period summaries.

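### SAP 12.3 scores the MAF Global Fatigue Index inconsistently: the rule read grammatically tops out at 40 and the one-line description at 144 to 150, against a stated maximum of 50

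*SAP*

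**What the plan says.** SAP section 12.3 makes three statements about the size of the GFI.

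- The range: "Scores range from 1-no fatigue to 50-severe fatigue".
- A one-line description: "MAF scoring is a sum of the responses to questions 1-15".
- The calculation: "converting item 15 to a 0-10 scale by multiplying each score by 2.5", then "summing items 1, 2, and 3; and averaging items 4-14 and the newly score item 15".

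On the inputs, it says: "Subjects rate each item 1 through 14 using a 10-point numeric rating scale, and items 15 and 16 using categorical responses for timing". It also says: "Item 16 is not included in the GFI". A subject who answers 1 (not at all) to item 1 stops there, is given 0 on the remaining items and scores 1. An activity item (4-14) gets no score if the subject does not do that activity for reasons other than fatigue.

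The GFI is listed as a patient-reported endpoint in SAP 4.8. Observed values, change and percent change are summarized for both the double-blind and open-label periods. SAP section 12 adds: "No formal hypothesis-testing analysis of PRO data will be performed". Protocol section 9.4.3 describes the items but gives no formula and no score range.

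**The concern.** The range and the two scoring statements sit in one section and should describe the same score. As worded, the calculation makes items 4-14 and rescaled item 15 joint objects of the averaging, so the whole averaged block can add no more than 10 points to the sum of items 1-3. That does not reach 50. The plain-sum sentence overshoots it by a wide margin.

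Nothing else in the documents settles which is meant. SAP 12.1 sends SF-36 scoring to licensed software and SAP 12.5 sends MOS-12 scoring to a reference manual, but SAP 12.3 names no scoring source for the MAF. Its text is therefore the specification a programmer would work from. The GFI is the only MAF result to be reported, so a mis-scaled GFI leaves no other MAF summary to fall back on.

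**Working it through.** **Inputs, all from SAP 12.3**

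- Items 1-14: 10-point scale, so at most 10 each.
- Item 15: raw score × 2.5, on 0-10, so at most 10. The raw coding of 0 to 4 is inferred from the multiplier and the 0-10 range (4 × 2.5 = 10).
- Item 16: excluded.

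**Step 1. Try to reproduce the stated maximum of 50**

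| Rule | Calculation at the ceiling | Maximum |
|---|---|---|
| Sum of 1-3, plus average of 4-14 and rescaled 15 (grammatical reading) | 3×10 + (11×10 + 10)/12 | 40 |
| Plain sum of 1-15, item 15 rescaled | 14×10 + 10 | 150 |
| Plain sum of 1-15, item 15 raw | 14×10 + 4 | 144 |
| Mean of 1-3, plus average of 4-14 and rescaled 15 | 10 + 10 | 20 |
| Sum of 1-3, plus mean of 4-14, plus rescaled 15 | 30 + 10 + 10 | 50 |

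Only the last rule gives 50. Under the stop rule it gives 1 + 0 + 0 = 1, so the stated minimum holds as well. The 40 in the first row does not depend on how many activity items are scored, because every element of the average has the same maximum of 10.

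**Step 2. Effect on a score**

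Let k be the number of scored activity items, m their mean and r the rescaled item 15. The additive score (last row) minus the literal score (first row) is

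m + r − (k·m + r)/(k + 1) = m/(k + 1) + r·k/(k + 1).

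This is never negative, so the literal rule never gives the higher value. At m = r = 10 the gap is 10 points.

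Take items 1-3 at 6 each, items 4-14 at 5 each and raw item 15 at 3, so r = 7.5.

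- Literal: 18 + (55 + 7.5)/12 = 23.2.
- Additive: 18 + 5 + 7.5 = 30.5.
- Gap: 5/12 + 7.5 × 11/12 = 7.3, which agrees.

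**Step 3. Effect on change, from the same starting point**

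- Item 15 improves by one category and nothing else moves: −2.5/12 = −0.21 literal, −2.5 additive. The literal rule understates the change.
- Items 1-3 fall by 3 points in total while item 15 worsens by one category: −3 + 0.21 = −2.79 literal, −3 + 2.5 = −0.5 additive. The literal rule overstates the improvement.
- Items 1-3 fall by 3 points in total and nothing else moves: −3/23.2 = −12.9% literal, −3/30.5 = −9.8% additive. The absolute change is the same, but the percent change is larger under the literal rule because its baseline is smaller.

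**Step 4. Weight of item 15**

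Under the literal rule item 15 has weight 1/(k + 1) within the averaged block: 1/12 with all 11 activities scored, 1/6 with five. Because k depends on which activities a subject does, the weight can differ between subjects, and between visits for one subject. In the example, going from k = 11 to k = 5 with every scored answer unchanged moves the block from 62.5/12 = 5.21 to 32.5/6 = 5.42.

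**The case against.** The best defence is that the sentence is a badly punctuated list that never says how its parts are combined; even the 40 needs an implied plus sign. It can be stretched to three components (the sum of items 1-3, the average of items 4-14, and the newly scored item 15), and that reading gives 50. Rescaling item 15 to 0-10 is also compatible with using it as a separate component. This stands as a likely account of the intent. It does not clear the text: the grammar points the other way, the plain-sum sentence remains wrong on either reading, and a scoring rule should not have to be decoded from its range.

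A second defence is that a programmer would see the 50-point range and that SAP section 14 requires program qualification and independent review of output. That lowers the risk. It does not remove it, because two programmers could share the literal reading, and a sample with nobody near the ceiling might not expose it.

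Three stronger inferences are tempting, and the documents do not support them.

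- *A wrong GFI will certainly be produced.* The text creates a risk; what the program does is not known.
- *Changes are understated in general.* Values are never higher under the literal rule, but step 3 shows change and percent change moving either way.
- *Item 15 always carries 1/12 of the averaged block.* That holds only when all 11 activity items are scored.

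**Conclusion.** The inconsistency is real. The grammatical reading of the rule has a maximum of 40 and the plain sum 144 to 150, while the stated range ends at 50. If the rule is programmed literally, GFI values fall below the range-consistent score by as much as 10 of 50 points at the ceiling (7.3 points in the worked example), and change and percent change are mis-scaled in a direction that depends on which items move.

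The consequence is limited. The GFI is a descriptive patient-reported outcome, outside the primary, key secondary and secondary efficacy endpoints and outside the multiplicity procedure. A reader might infer some threat to the trial's efficacy conclusions; there is none.

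The conclusion rests on a maximum of 10 for each of items 1-14 and for rescaled item 15, both taken from SAP 12.3. The raw 0-4 coding of item 15 is an inference; it affects the 144 figure and the size of one category step, not the 40 or the 50. The additive formula is likewise inferred: it is the only variant tried that matches the stated range, but the instrument's scoring instructions are not in the documents.

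**What to change.** In SAP 12.3, replace the calculation sentence with an explicit formula: GFI = item 1 + item 2 + item 3 + mean of scored items 4-14 + (item 15 × 2.5), range 1 to 50. Delete the sentence describing the score as a sum of items 1-15. State the raw coding of item 15, and what happens when none of items 4-14 is scored, since the mean is then undefined. Before finalizing, confirm the formula against the instrument's scoring instructions, cite that source in the section, and check that the analysis program follows it.

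The cost is an edit to one paragraph and a program check. No new data are needed and no tested analysis changes.

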### **12.4. Psychological General Well-Being Index (PGWBI)**

The Psychological General Well-Being Index (PGWBI) is a validated 22-item scale that assesses psychological and general well-being in 6 domains: anxiety (5 questions), depressed mood (3 questions), positive well-being (4 questions), self-control (3 questions), general health (3 questions) and vitality (4 questions). Each question has a response option on 6-point Likert scale (0-5 in value) with a one month recall period. A high score means higher level of psychological wellbeing. The scores for all domains can be summed to provide a maximum score (up to 110 points).

Scoring for the PGWBI consists of 1 total score, ranging from 0-110 (22 questions X 0-5 per question) as well as 6 sub health scores.

**Table 10: PGWBI Sub Health Scores**

Health State	Number of Questions	Score Range
Anxiety	5	(5 x 5) = 0-25
Depressed Mood	3	(3 x 5) = 0-15
Positive well-being	4	(4 x 5) = 0-20
Self-Control	3	(3 x 5) = 0-15
General health	3	(3 x 5) = 0-15
Vitality	4	(4 x 5) = 0-20

The observed and change from baseline values for the PGWBI total scores and 6 sub scores will be summarized descriptively by treatment group for the DB period and the OL period. The study baseline will be used for the DB period, and the OL baseline will be used for the OL period summaries.

## 12.5. Medical Outcomes Study 12-Item Sleep Scale (MOS-12)

The Medical Outcomes Study 12-item Sleep Scale (MOS-12) is a reliable, valid tool for assessing changes in sleep. The MOS-12 is a subject-reported, non-disease-specific instrument for evaluating sleep outcomes and consists of 12 items to measure 6 sleep dimensions. The recall timeframe is the past four weeks.

The MOS-12 yields 6 scale scores:

- Sleep disturbance, which measures the ability to fall asleep and maintain restful sleep (4 items)
- Sleep adequacy, which measures the sufficiency of sleep in terms of sleeping enough to provide restoration of wakefulness (2 items)
- Sleep quantity, which measures (in hours) the amount of sleep an individual has had each night (1 item)
- Somnolence, which measures daytime drowsiness or sleepiness (3 items)
- Snoring (1 item)
- Shortness of breath, or headache (1 item)
- 

Each item within a domain (except sleep quantity) is recalibrated on a 0-100 scale (with 0 as the lowest possible score and 100 as the highest possible score). Items within each scale (as bulleted above) are averaged together to create the 6 scale scores. Items that are left blank (missing data) are not used when calculating the scale scores. Scores represent the average for all items in the scale that the respondent answered. Note that the 6 scale scores will not be calculated or summarized as the CRFs collected data following the unrevised, older version of the MOS-12 scale.

The sleep problems index II uses 9 of the 12 items of the scale to compute an overall sleep problem summary. This index contains questions from the sleep disturbance, sleep adequacy, respiratory impairment, and somnolence domains but does not include the question on sleep quantity. The 3 questions in index II not included in index I are time to fall asleep, feeling that sleep was quiet, and feeling drowsy or sleepy during the day. Scoring of the MOS-12 will be based on the reference manual.

The observed, change from baseline, and percent change from baseline values for the quantity of sleep and the 2 sleep problem indices will be summarized with descriptive statistics by treatment group for the DB period and the OL period. The study baseline will be used for the DB period, and the OL baseline will be used for the OL period summaries.

